7.3 Clinical Laboratory Assessments

Clinical laboratory tests will be obtained at the time points presented in Appendix A. Continuous clinical laboratory values will be summarized by presenting descriptive statistics of raw data and change from baseline values at each time point for each treatment group. Qualitative results at each time point measured will be summarized by presenting the number and percentage of subjects for each category.

Assessments from selected chemistry and hematology parameters can be graded based on the RCTC grading for laboratory data presented in the protocol Appendix B. A frequency distribution of the RCTC v2.0 severity at baseline, at each post-baseline assessment, and the worst value after baseline will be prepared. For each assessment after the baseline value the table will also provide the frequency of subjects with data, the frequency of subjects with Grade 3 or 4, and the frequency

of subjects with Grade 3 or 4 adjusted for baseline. For the latter frequency, subjects must have a baseline value and a value at the post-baseline time point, and subjects with the same or worse toxicity grade at baseline are not considered. Results will be tabulated and presented using counts and frequencies.

A listing of lab results with grade 1 or higher toxicity will also be provided.

7.4 Vital Signs

Descriptive summaries of the vital signs (both raw and change from baseline values) including systolic and diastolic blood pressure, heart rate, respiratory rate, and body temperature will be prepared for each treatment group by visit. Descriptive statistics for quantitative variables will include n, mean, standard deviation, median, minimum, and maximum. The 95% confidence interval of the mean will be constructed if it is appropriate (when there is more than 1 subject in a treatment group).

Vital sign values will be classified as low, normal or high based on the cut-off points defined below, and the data will be summarized by presenting shift tables from baseline to each post-baseline visit. Unscheduled visits will be excluded from the summaries but will be included in the data listings.

For Baseline vital sign measurements:

Measurement	Lower	Upper	Unit
Temperature	<35.0	>38.0	C
Systolic Blood Pressure (BP)	<110	>135	mmHg
Diastolic BP	<65	>85	mmHg
Heart Rate	<50	>110	beats/min
Respiratory Rate	<12	>20	breaths/min

For Post-baseline vital sign measurements:

Measurement (unit)	Low	High
Temperature (C)	<35	>38
Systolic Blood Pressure (mm Hg)	≥ 20 point decrease from baseline	≥ 20 point increase from baseline
Diastolic Blood Pressure (mm Hg)	≥ 20 point decrease from baseline	≥ 20 point increase from baseline
Pulse (beats per minute (bpm))	< 50 and decrease from baseline ≥ 15	> 100 and increase from baseline ≥ 15
Respiratory Rate (breaths per min)	<12	>20

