9.5.6 Vital Signs

Descriptive summaries of the vital signs (both raw and change from baseline values) including blood pressure, heart rate, respiratory rate, and body temperature will be prepared for each dose group. Descriptive statistics for quantitative variables will include sample size, mean, standard deviation, standard error, median, minimum, and

maximum. The 95% confidence interval of the mean will be constructed if it is appropriate (when there is more than 1 subject in a cohort).

Vital sign values will be classified as low, normal or high based on the cut-off points defined below, and the data will be summarized by presenting shift tables from baseline to each post-baseline visit. For Baseline vital sign measurements:

Measurement	Lower	Upper	Unit
Temperature	<35.0	>38.0	С
Systolic Blood Pressure (BP)	<110	>135	mmHg
Diastolic BP	<65	>85	mmHg
Heart Rate	<50	>110	beats/min
Respiratory Rate	<12	>20	breaths/min

For Post-baseline vital sign measurements:

Measurement (unit)	Low	High
Systolic Blood Pressure (mm Hg)	≥ 20 point decrease from baseline	≥ 20 point increase from baseline
Diastolic Blood Pressure (mm Hg)	≥20 points decrease from baseline	≥ 20 point increase from baseline
Pulse (beats per minute (bpm))	< 50 and decrease from baseline ≥ 15	> 100 and increase from baseline ≥ 15
Temperature (C)	<35	>38
Respiratory Rate (breaths per min)	<12	>20

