A4. Serum sickness	Transient, non-prescription	Symptomatic, slow response to	Prolonged; symptoms only	Major organ dysfunction, requires
	meds relieve	meds (e.g. oral corticosteroids)	partially relieved by meds;	long-term high-dose
			parenteral corticosteroids	immunosuppressive therapy
			required	

	1- Mild	2- Moderate	3- Severe	4- Includes Life Threatening
A. ALLERGIC/IMMUNOLOG	IC (CONT)			
A5. Vasculitis	Localized, not requiring treatment; or rapid response to meds; cutaneous	Symptomatic, slow response to meds (e.g. oral corticosteroids)	Generalized, parenteral corticosteroids required or/and short duration hospitalisation	Prolonged, hospitalization, ischemic changes, amputation
B. CARDIAC				
B1. Arrhythmia	Transient, asymptomatic	Transient, but symptomatic or recurrent, responds to meds	Recurrent/persistent; maintenance prescription	Unstable, hospitalization required; parenteral meds
B2. Cardiac function Decreased	Asymptomatic decline in resting ejection fraction by > 10%, but < 20% of baseline value	Asymptomatic decline of resting ejection fraction ≥20% of baseline value	CHF responsive to treatment	Severe or refractory CHF
B3. Edema	Asymptomatic (e.g. 1 + feet/calves), self-limited, no therapy required	Symptomatic (e.g. 2 + feet/calves), requires therapy	Symptoms limiting function (e.g. 3 + feet/calves, 2 + thighs), partial relief with treatment, prolonged	Anasarca; no response to treatment
B4. Hypertension (new onset or worsening)	Asymptomatic, transient increase by > 20 mm Hg (diastolic) or to > 150/100 if previously normal, no therapy required	Recurrent or persistent increase > 150/100 or by > 10 mm Hg (diastolic), requiring and responding readily to treatment	Symptomatic increase >150/100, > 20 mmHg, persistent, requiring multi-agent therapy, difficult to control	Hypertensive crisis
B5. Hypotension (without underlying diagnosis)	Transient, intermittent, asymptomatic, orthostatic decrease in blood pressure > 20 mm Hg	Symptomatic, without interference with function, recurrent or persistent > 20 mm Hg decrease, responds to treatment	Syncope or symptomatic, interferes with function, requiring therapy and sustained medical attention, dose adjustment or drug discontinuation	Shock

FINAL / Version 5.0 1-AUGUST-2018

	1- Mild	2- Moderate	3- Severe	4- Includes Life Threatening
B. CARDIAC (CONT)		•		

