7. SAFETY ANALYSIS

Safety assessments will include assessment of DLT, AEs, chemistry, hematology (complete blood count and differential), coagulation profile, urinalysis, and vital signs. All safety summaries (or analyses if applicable) will be conducted using the SAF set. No formal hypothesis testing will be performed to compare differences between treatment groups.

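### The blood-pressure and pulse shift tables use different definitions of Low/Normal/High before and after baseline, so unchanged abnormal values are tabulated as moving to Normal

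*SAP*

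**What the plan says.** In SAP 7.4 Vital Signs, measurements are to be "classified as low, normal or high based on the cut-off points defined below, and the data will be summarized by presenting shift tables". Each table sets the baseline category against the category at a later visit. Protocol 9.5.6 has the same rule ("the data will be summarized by presenting shift tables from baseline to each post-baseline visit") and the same two sets of cut-offs.

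| Measure | Baseline Low / High | Post-baseline Low / High |
|---|---|---|
| Systolic BP (mmHg) | <110 / >135 | fall of at least 20 / rise of at least 20 |
| Diastolic BP (mmHg) | <65 / >85 | fall of at least 20 / rise of at least 20 |
| Pulse (beats/min) | <50 / >110 | <50 with a fall of at least 15 / >100 with a rise of at least 15 |
| Temperature (C) | <35 / >38 | <35 / >38 |
| Respiratory rate (breaths/min) | <12 / >20 | <12 / >20 |

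The post-baseline High entry for both pressures is "≥ 20 point increase from baseline", with no absolute limit. For pulse the entries are "< 50 and decrease from baseline ≥ 15" and "> 100 and increase from baseline ≥ 15". Neither document defines post-baseline Normal separately or gives a rule for values already abnormal at baseline.

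**The concern.** A shift table is read on the understanding that a category means the same thing on both axes. Here that holds for temperature and respiratory rate, but not for blood pressure or pulse. A subject whose blood pressure is high at entry and does not move has a change of zero. That subject cannot be Low or High after baseline and so falls into Normal. The table then reports a normalisation that did not occur.

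The measure is not incidental. Protocol 1.4.1 lists a temporary rise in blood pressure as a possible risk if burning pain is severe. The entry criteria admit ages 35 to 75 and, for blood pressure, exclude only labile or poorly controlled hypertension, so baseline systolic values above 135 are plausible. Vital signs are recorded on Days 1-4 (pre-dose and 90 minutes after application) and on Days 5 and 94, so the mislabelling would recur across the post-baseline visits tabulated.

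**Working it through.** **1. The rules applied literally.** The inputs are the cut-offs in the table above, with Normal meaning neither Low nor High. Every abnormal whole-number baseline value in a wide range was carried forward unchanged (temperature in steps of 0.1).

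| Measure (range) | Abnormal baseline values | Labelled Normal when unchanged |
|---|---|---|
| Systolic 70-220 | 40 below 110 + 85 above 135 = 125 | 125 |
| Diastolic 40-130 | 25 + 45 = 70 | 70 |
| Pulse 35-160 | 15 + 50 = 65 | 65 |
| Respiratory rate 6-35 | 6 + 15 = 21 | 0 |
| Temperature 34.0-40.0 | 10 + 20 = 30 | 0 |

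For blood pressure and pulse this holds at any value, because a change of zero meets neither the 20-point nor the 15-beat criterion.

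**2. Individual cases.**
- Systolic 150 to 150: High to Normal. So is 150 to 169, since +19 is below 20.
- Pulse 115 to 115: High to Normal. Pulse 45 to 45: Low to Normal.
- Systolic 160 to 140: change -20, so High to Low, although 140 is above 135.
- Systolic 100 to 120: change +20, so Low to High, although 120 lies within 110-135.
- Systolic 130 to 149: change +19, so Normal to Normal, although 149 is above 135.

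**3. Illustrative size for systolic pressure.** The documents give no mean or SD, so all inputs here are assumptions: no true change; mean m of 125, 130 or 135; between-subject SD b of 14 or 16; visit-to-visit SD v of 5, 8, 10 or 12 (24 combinations). Let X0 and X1 be the baseline and later values, bivariate normal with the same mean m.
- Total SD: t = √(b² + v²). Correlation: r = b²/t².
- X1 given X0 = x is normal with mean m + r(x − m) and SD t√(1 − r²).
- As written: P(−20 < X1 − X0 < 20 | X0 > 135).
- Same limits: P(110 ≤ X1 ≤ 135 | X0 > 135).

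Worked case, m = 130, b = 14, v = 8: t = √260 = 16.12; r = 196/260 = 0.754; conditional SD = 16.12 × √(1 − 0.568) = 10.6. P(X0 > 135) = 1 − Φ(5/16.12) = 0.378, or 15.1 of 40. Integrating over X0 > 135 gives 91.7% labelled Normal as written, against 28.4% with the same limits.

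| Visit SD | Baseline-High to Normal: as written | Same limits | Baseline-Low to Normal: as written | Same limits |
|---|---|---|---|---|
| 5 | 99.4-99.5% | 13.5-24.2% | 99.1-99.4% | 24.3-39.0% |
| 8 | 90.9-92.3% | 20.3-34.4% | 86.7-90.6% | 34.8-52.1% |
| 10 | 81.7-84.3% | 23.7-38.2% | 74.5-81.0% | 38.8-54.6% |
| 12 | 72.7-76.1% | 26.1-40.0% | 63.5-71.7% | 40.6-53.5% |

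The gap for baseline-High subjects is 33 to 86 points. The same-limits figure is not zero because visit-to-visit variation alone carries some subjects back across 135.

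**4. Sensitivity to the assumed mean.** With m of 115-120, b of 8-12 and v = 8, only about 1.5 to 6 subjects per 40 are High at baseline, and the gap narrows. It is 78.0% against 73.9% at m = 115, b = 8, and 88.6% against 47.5% at m = 120, b = 12. The figures in step 3 are therefore not bounds.

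**The case against.** The strongest reply is that this is a labelling matter. Post-baseline Normal is never defined and no table shells are in the two documents, so the final column headings are unknown. Every cut-off is printed openly under separate baseline and post-baseline headings. Change-based flags are also a reasonable way to look for a treatment-related rise in pressure. Part of this stands. The change criteria are legitimate and should be kept, and reading Normal as the remainder is an inference. But the plan offers three categories and defines two of them, so no other reading is available.

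A second reply is that little is at stake, and that also stands. SAP 7 says "No formal hypothesis testing will be performed to compare differences between treatment groups". SAP 7.4 also plans "Descriptive summaries of the vital signs (both raw and change from baseline values") by treatment group and visit, and subject data are listed. Hypertension is graded on its own criteria in protocol Appendix B (Grade 2 begins "Recurrent or persistent increase > 150/100 or by > 10 mm Hg (diastolic") and is named under dose-limiting toxicity in protocol 3.2, with dose-limiting toxicities tabulated under SAP 7.2.5.

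Two stronger readings are tempting. A reader might infer that the tables hide large blood-pressure rises. They do not: a rise of 20 points or more is labelled High whatever the baseline. A reader might also infer that the pulse limits of 110 and 100 contradict each other. They sit in different rules, one absolute and one compound, so they differ between axes without being a separate contradiction. They need reconciling only if a single pair is to serve both axes.

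**Conclusion.** The rule is wrong as written, and the consequence is minor. Followed literally, both documents produce a blood-pressure and pulse shift table in which every unchanged abnormal value is shown as becoming Normal and some labels point the wrong way. That conclusion rests only on the printed cut-offs and on Normal being the remainder category.

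The percentages rest on assumed blood-pressure distributions and show how large the effect could be, not how large it will be; a lower mean pressure would give fewer baseline-High subjects. The documents do not support inferring a distorted comparison between arms or any effect on efficacy. The rule is the same in every arm, and the damage is confined to how one descriptive safety table would be read. Temperature and respiratory rate are unaffected.

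**What to change.** In both SAP 7.4 and protocol 9.5.6:

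- Use one set of absolute cut-offs on both axes of the blood-pressure and pulse shift tables. For systolic and diastolic pressure these can be the plan's own baseline limits. For pulse, the authors should reconcile the 110 and 100 upper limits and use a single pair.
- Report the existing change-based criteria in a separate table by arm and visit, labelled 'notable decrease' and 'notable increase'.
- Leave temperature and respiratory rate as they are.

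If only one table is wanted, the minimum correction is to rename the post-baseline blood-pressure and pulse columns 'notable decrease / neither / notable increase' and footnote both definitions.

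With the same limits on both axes, the false shifts counted in step 1 fall to zero, because an unchanged value stays in its own category. The cost is one extra descriptive table, or relabelled columns and a footnote, with matching wording in the two documents. No new data are needed and no efficacy analysis changes.

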8. INTERIM ANALYSES

The scope of this document details the final analysis to be performed by CTI, and does not describe any interim analysis that may be performed.

9. SAMPLE SIZE AND POWER CALCULATIONS

A sample size analysis has been performed and suggests that a sample size of 40 evaluable subjects per each of the three study arms will appropriately power this study. WOMAC pain subscale includes 5 components ranging from 0 to 500 points. The table below shows that 40 subjects per treatment group would provide 80% power to detect a difference of 63 between the treatment arms with respect to change from baseline in WOMAC pain score, assuming the SD of the changes from baseline in WOMAC A is 100.

Power to Detect Difference Δ Between Treatments With Respect to Changes from Baseline (2-sided $\alpha = 5\%$, $n=40$ /Group)										
SD (CFB†)	$\Delta =$ Treatment Difference Between Mean Changes from Baseline									
	25	30	35	40	45	50	55	60	63	65
100	20%	27%	35%	43%	52%	61%	69%	77%	80%	83%
105	19%	25%	32%	40%	48%	57%	65%	72%	77%	79%
110	17%	23%	30%	37%	45%	53%	61%	68%	73%	75%

†CFB = Change from Baseline, SD(CFB) = Standard Deviation of CFB

11. APPENDIX

11.1 Appendix A: Schedule of Events

Assessment	SCR	Treatment Days				Follow-up Period Days					
		Within 28 days of Day 1	D1	D2	D3	D4	D5 (Post Treat Day 1)	D19± 3d (Post Treat Week 2)	D35± 3d (Post Treat Week 4)	D64± 3d (Post Treat Week 8)	D94± 3d (Post Treat Week 12)
Clinic visit	x	x	x	x	x	x	x	x	x	x	x
Informed Consent	x										
Inclusion / Exclusion	x										
Demographics	x										
Medical & Medication History	x										
Randomization		x									
Physical exam	x										x
Height and Weight ^a	x										
Vital Signs ^b	x	x	x	x	x	x				x	x
Knee X-rays ^c	x										
12-lead ECG ^d	x										
Clinical lab tests ^e	x					x		x		x	x
Pregnancy or FSH Test ^f	x	x									
Application Site Pain, Erythema, Scaling, Pruritus Assessment ^g	x	x	x	x	x	x	x	x	x	x	x
Exploratory Assessment of OA Knee Pain ^h	x	x									
VAS OA Knee Pain Assessment ⁱ		x	x	x	x	x	x	x	x	x	x
WOMAC ^j	x	x				x	x	x	x	x	x
Drug administration		x	x	x	x						
Assess. Of Concomitant Medications ^k	x	x	x	x	x	x	x	x	x	x	x
AE Assessments		x	x	x	x	x	x	x	x	x	x
Study Exit										x	

Schedule of Events (Continued)

- a. Height and weight obtained at Screening.
- b. Vital signs include temperature, blood pressure, heart rate and respiratory rate. Performed at Screening, on Days 1-4 at pre-dose and at 90 minutes (± 5 min) after applying study drug to knees, and at Follow-up on Day 5 and 94.
- c. Knee X-rays of both knees must be obtained unless films/images performed within 6 months before screening. Copies of film and results will be requested.
- d. Standalone 12-lead ECG performed at Screening.
- e. Clinical laboratory tests include (Appendix A):
 - Hematology: full blood count including RBC, hemoglobin, hematocrit, MCV, MCH, MCHC, WBC, differential white cell count, platelet count (Screening, Day 5, Day 35 and Day 94);
 - Erythrocyte sedimentation rate (Screening only):
 - Chemistry: BUN, creatinine, uric acid, bilirubin (total), sodium, potassium, calcium, magnesium, phosphorous (inorganic), chloride, bicarbonate, ALK, AST (SGOT), ALT (SGPT), LDH, GGT, CPK, albumin, total protein, and glucose (Screening, Day 5, Day 35 and Day 94);
 - IgM RF (Screening only):
 - Urinalysis: pH, protein, glucose, ketones, bilirubin, blood, urobilinogen, specific gravity, leucocytes (Screening, Day 5, Day 35 and Day 94). Clinically significant abnormal dipstick results will require microscopic analysis.
- f. Serum pregnancy test at Screening and urine pregnancy test at baseline on Day 1 for premenopausal women; FSH (follicle stimulating hormone) test at Screening to confirm postmenopausal status (females only) for up to 2 years after cessation of menses.
- g. Application site pain will be assessed on NRS (0-10); application site erythema/edema will be assessed using modified categorical Draize test (0-3). Scaling and pruritus will also be scored on a similar categorical scale (0-3). Scoring for application site pain (not related to knee pain) will be performed on drug administration Days 1-4 (pre-application [≤ 30 min], and at 15 (± 5 min), 30 (± 5 min), 60 (± 5 min) and 90 minutes (± 5 min) after application) and on Days 5, 19, 35, 64 and 94. Application site skin reactions (erythema, edema, scaling, pruritus) will be assessed on drug administration Days 1-4 at pre-application (≤ 30 min), and at 15 (± 5 min), 30 (± 5 min), 60 (± 5 min) and 90 minutes (± 5 min) after application), and on Days 5 (24 hrs [± 4 hrs]), 19 (± 3 days), 35 (± 3 days), 64 (± 3 days) and 94 (± 3 days). (Appendix E and Appendix F)
- h. Exploratory assessment of OA knee pain (average daily pain and daily worst pain) at Screening and Day 1 (pre-application [≤ 30 min]) (Appendix D).
- i. OA Knee pain to be scored on 100 mm VAS scale (Appendix G) pre-treatment (≤ 30 min) on Days 1, 2, 3 and 4 and also on clinic visits at Days 5 (24 hrs [± 4 hrs]), 19 (± 3 days), 35 (± 3 days), 64 (± 3 days) and 94 (± 3 days).
- j. WOMAC Pain, Stiffness, and Physical Function will be performed at Screening and on Day 1 prior to drug administration (≤ 30 min) and on Days 5 (24 hrs [± 4 hrs]), 19 (± 3 days), 35 (± 3 days), 64 (± 3 days) and 94 (± 3 days).
- k. Document all medications taken within 90 days of the Screening Visit through Day 94.
- l. Refer to Section 6.5 for assessments to be completed at time of SAE, early termination or unscheduled visit.
